### **2.6.5.2 Vital signs**

Data on vital signs will be tabulated and summarized descriptively as follows:

- Number and percentage of patients who shift from non-notable at baseline to notable post- baseline. Also, bar chart with 95% CI will be presented for the notable changes.

The number and percentage of patients with notable vital sign values (high/low) in systolic blood pressure, diastolic blood pressure, pulse rate, weight and temperature will be presented by Cohort.

A listing of notable vital sign values will be produced. In the listing, the assessments collected outside of on-treatment period will be flagged.

### **2.6.5.3 Cardiovascular and Pulmonary risk factor assessment**

Prior to random allocation of patients to cohort and at the end of treatment, cardiovascular risk factors collected will be listed by cohort.

Prior to random allocation of patients to cohort and at Week 20, pulmonary function tests including assessment of the lung volumes FEV1, FVC, FEV1/FVC, TLC, VC and DLCO will be performed, if clinically indicated. A listing will be presented by cohort.

## **2.7 Analysis of the key secondary objective**

Not applicable

## **2.8 Analysis of the secondary objective(s)**

The secondary objective(s) of the study are:

- To estimate the rate of hematologic and molecular responses at specific time points for
- Cohort A, B and C
- Rate of CHR, MR2, MMR, MR4, MR4.5 in 12, 24, 48, 72 weeks of therapy
- To estimate time to hematologic and molecular response
- Time to CHR, MR2, MR4, MR4.5 in 12, 24, 48, 72 weeks of therapy

- To evaluate the duration of hematologic and molecular response
- Duration of MR1, MR2, MMR, MR4 and MR4.5
- To evaluate Progression Free Survival (PFS)
- To evaluate Overall Survival (OS)

### **2.8.1 Secondary safety endpoints**

The secondary safety endpoints are:

- AEs, SAEs and laboratory evaluation for Cohort A, Cohort B and Cohort C, by 48, 72 weeks

All secondary safety analysis will be performed similar to the above primary safety analysis using Safety set (SS) by 48, 72 weeks. Additionally, a separate safety summary up to 24 weeks will be provided for Cohort C.

### **2.8.2 Secondary efficacy endpoints**

The secondary efficacy endpoints are:

- Rate of CHR, MR2, MMR, by 12, 24, 48, 72 weeks of therapy
- Rate of MR4, MR4.5 by 24, 48, 72 weeks of therapy
- Time to CHR, MR2, MMR, MR4, MR4.5
- Duration of CHR, MR2, MMR, MR4 and MR4.5
- PFS during 24, 48 and 72 weeks
- OS during 24, 48 and 72 weeks

For all secondary efficacy analyses, the Full Analysis Set (FAS) will be used, unless stated otherwise.

For secondary efficacy analysis, proportion of patients achieving the response levels will be presented together with an exact 95% Clopper-Pearson confidence interval. For time to event and duration, PFS & OS, median, 25th percentile & 75th percentile will be reported along with their respective 95% Confidence Interval.

#### **Rate of CHR, MR2, MMR, by 12, 24, 48, 72 weeks of therapy and Rate of MR4 & MR4.5 by 24, 48, 72 weeks of therapy**

- The rate of **Complete Hematologic Response (CHR)** by 12, 24, 48 and 72 weeks. **CHR** is defined as all of the following present for  $\geq 4$  weeks:
  - WBC count  $< 10 \times 10^9/L$
  - Platelet count  $< 450 \times 10^9/L$
  - Basophils  $< 5\%$
  - No blasts and promyelocytes in peripheral blood
  - Myelocytes + metamyelocytes  $< 5\%$  in peripheral blood
  - No evidence of extramedullary disease, including spleen and liver
- The rate of **molecular response (MR2)** by 12, 24, 48 and 72 weeks after the start of first study medication. **MR2** is defined as  $\geq 2$  log reduction of BCR-ABL transcript from standardized baseline or  $\leq 1\%$  BCR-ABL/ABL % by international scale, measured by real-time quantitative PCR (RQ-PCR).

- The rate of **major molecular response (MMR)** by 12, 24, 48 and 72 weeks after the start of first study medication. MMR is defined as  $\geq 3$  log reduction of BCR-ABL transcript from standardized baseline or  $\leq 0.1\%$  BCR-ABL/ABL % by international scale, measured by real-time quantitative PCR (RQ-PCR).
- The rate of **molecular response (MR4)** by 24, 48 and 72 weeks after the start of first study medication. **MR4** is defined as  $\geq 4$  log reduction of BCR-ABL transcript from standardized baseline or  $\leq 0.01\%$  BCR-ABL/ABL % by international scale, measured by real-time quantitative PCR (RQ-PCR).
- The rate of the **molecular response (MR4.5)** by 24, 48 and 72 weeks after the start of first study medication. **MR4.5** is defined as  $\geq 4.5$  log reduction of BCR-ABL transcript from standardized baseline or  $\leq 0.0032\%$  BCR-ABL/ABL % by international scale, measured by real-time quantitative PCR (RQ-PCR).

For rate of MR2, MMR, MR4, MR4.5 by any pre-specified time point patients will be considered as responder if he/she achieves the particular response at least once by the specific timepoint. If patient discontinuing the treatment prior to a specific time point due to any reason and not achieved the particular response before the discontinuation will be considered as non-responder.

For each time point, the proportion of patients achieving the specific response levels will be presented together with an exact 95% Clopper-Pearson confidence interval by cohort. The rates over time will be displayed graphically using the Bar Charts with 95% C.I. as whiskers.

**Note:** Patient(s) who have reported for molecular response(s) at baseline will not be included in time to event analyses.

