## 2.2 Analysis sets

### Full Analysis Set (FAS)

The Full Analysis Set (FAS) comprises all patients to whom study medication has been assigned. According to the intent to treat principle, patients will be analyzed according to the study medication and Cohort they have been assigned.

All the secondary efficacy endpoints will be analyzed using FAS.

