#### 2.2.1 Subgroup analyses

Subgroup analyses will be performed based on the patient's baseline status:

- Age: (< 65 years; ≥ 65 years)
- Patients with resistance: (BCR-ABL ratio at baseline >10%)
- Previous treatment with Ponatinib (Yes or No)
- By number of prior TKI therapies: 2, 3, ≥4

Summary tables and figures will be generated only for subgroups with at least 5% of the total sample size of full analyses set (for efficacy endpoint) or safety set (for safety endpoint).

All primary and secondary endpoints will be analyzed and summarized within each subgroup. Additionally, as the study is ongoing during COVID-19 pandemic, to address the impact of COVID-19 (if any) AEs, SAEs, Abnormal lab findings and notable vital signs will be summarized and reported if COVID-19 infected patient count exceeds 5% of the total sample size of safety set.

As appropriate, given the significance of the impact of COVID-19 on the enrolled patients, a sensitivity analysis may be performed on the safety and efficacy data evaluating the impact of COVID-19 on the study, if COVID-19 infected patient count exceeds 5% of the total sample size.

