### **Time to CHR, MR2, MR4, MR4.5 in 72 weeks of therapy**

Time to achieving a response level is defined as the time from the date of the first dose of study medication to the first documented achievement of a response level.

Time to achieve a specific response level will be analyzed using the Kaplan-Meier Product-Limit method. Patients who are known to be without achieving that response level will be censored at the last molecular & hematologic assessment.

The estimated cumulative incidence rates and 95% confidence intervals at 12, 24, 48 and 72 weeks will be presented. The cumulative incidence curve will be plotted. , if applicable. The analyses will be performed using FAS by cohort.

For patients in the FAS who have not experienced any molecular and/or hematologic response, the time will be censored as follows in the Kaplan-Meier analysis:

- If a patient does not achieve the specified response before the cut-off date for the analysis, censoring time will be the last molecular assessment (PCR) date on treatment prior to the cut-off date or the EoT visit, whichever comes first.
- If a patient discontinues study treatment prior to achieving a response for a reason other than disease progression or death, then the patient will be censored at the last molecular assessment (PCR) date on treatment prior to the cut-off date or the EoT visit, whichever comes first.

- If a patient discontinues study treatment prior to achieving a response due to progression or death, then the censoring time will be set to the longest follow-up time in the treatment group, that is, consider the response is impossible to reach.

In case no on-treatment response assessment was performed, the patient will be censored at day 1.

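### The MR2, MMR, MR4 and MR4.5 rates by time point count patients already at that level at baseline, so on a plain reading they are 'achieved or maintained' rates presented as 'achieving' (minor)

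*SAP*

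**What the plan says.** The rates. Under the SAP 2.8.2 heading on response rates, for MR2, MMR, MR4 and MR4.5, "patients will be considered as responder if he/she achieves the particular response at least once by the specific timepoint". A patient who stops treatment before the time point and has "not achieved the particular response before the discontinuation will be considered as non-responder". Neither sentence refers to the patient's level at baseline.

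The analysis set. SAP 2.2 says "All the secondary efficacy endpoints will be analyzed using FAS", and SAP 2.8.2 says "For all secondary efficacy analyses, the Full Analysis Set (FAS) will be used, unless stated otherwise". The FAS is everyone assigned study medication. SAP 2.1 makes the cohort size the denominator for percentages.

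The levels. SAP Table 5-3 and Protocol 8.4.1 define each level by a fixed cut-off: 1% for MR2, 0.1% for MMR, 0.01% for MR4 and 0.0032% for MR4.5. The log reductions are measured from a standardized baseline, not from the patient's own baseline.

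Baseline responders. The only sentence about them is a note after the rates: "Patient(s) who have reported for molecular response(s) at baseline will not be included in time to event analyses". The time-to-response section that follows says "The analyses will be performed using FAS by cohort".

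Entry. Protocol 5.1, criterion 6, admits failure of, or intolerance to, the most recent TKI. Intolerance is defined by toxicity grade, with no minimum BCR-ABL1. One route to failure is loss of MMR after 12 months of therapy. Criterion 8 asks for a transcript type that can be quantified, not for a level.

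**The concern.** Take a patient who stopped the previous TKI for toxicity while in MMR. The baseline sample is at or below 0.1%, and so is the Week 4 sample. Under the SAP rule this patient has achieved MMR by Week 12, and remains a responder at Weeks 24, 48 and 72 even if the level is lost later. Similarly, a patient who enters through loss of MMR with a ratio above 0.1% but not above 1% is already in MR2.

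A reader of a table of patients achieving MMR will take it as response brought about by the study drug. The table cannot separate that from response carried in from earlier therapy, and the figure moves with the share of patients who enter in response. The note shows that the authors expected such patients, but it deals with them in a different analysis.

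The note also has a fault of its own: it names no level. Read literally, a patient in MR2 at baseline leaves every time-to-molecular-response analysis, including time to MMR, MR4 and MR4.5, although those levels have yet to be reached. Nor is it stated as an exception to the FAS in the section that follows.

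**Working it through.** The plan states no figure for this point. Its only design figure sets the cohort sizes used below, and it reproduces: 1.96² × 0.18 × 0.82 / 0.12² = 39.4, rounded up to 40; 40 / 0.90 = 44.4, rounded up to 45.

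**Inputs**
- Cohort sizes 45, 45 and 25 (SAP 3).
- b, the share of a cohort at the level at baseline: not in the documents. Any value is an assumption, and 0 is possible.
- r, the response rate among patients not at the level at baseline: not in the documents. As a rough stand-in for MMR without T315I I use 37% and 48% (Protocol 1.1.2.2, by 6 and 12 months). That source labels them as achieved or maintained, so they are themselves mixed rates. With T315I it gives 25% and 28%.

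**Per patient.** Counting one baseline responder as a responder rather than a non-responder, with the denominator unchanged, adds 1/45 = 2.2 points in Cohort A or B and 1/25 = 4.0 points in Cohort C.

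**General form.** If every baseline responder has at least one on-study sample at the level, the FAS rate is b + (1 − b)r. Its excess over r is b(1 − r).

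| Assumed b | r = 37% | r = 48% |
|---|---|---|
| 0 | 0 | 0 |
| 5% | 3.15 points | 2.6 points |
| 10% | 6.3 points | 5.2 points |
| 20% | 12.6 points | 10.4 points |

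With T315I, r of 25% and 28% gives 3.75 and 3.6 points at b = 5%, and 7.5 and 7.2 at b = 10%. These are the least supported values, because Protocol 1.2 describes T315I as resistant to every TKI except ponatinib. The documents give no MR4 or MR4.5 rates, so only the per-patient step applies there.

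**Illustration.** A cohort of 45 has 4 patients in MMR at baseline, all keeping it for one sample, and 16 new responders.
- Rule as written: 20/45 = 44.4% (Clopper-Pearson 95% interval 29.6 to 60.0).
- Patients not in MMR at baseline: 16/41 = 39.0% (24.2 to 55.5).
- Baseline responders counted as non-responders: 16/45 = 35.6% (21.9 to 51.2).

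The first two differ by 5.4 points, which agrees with b(1 − r) = 0.089 × 0.610.

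**Do other planned outputs show new response?**
- The cumulative incidence at 12, 24, 48 and 72 weeks does so in part. Its section heading omits MMR, but time to MMR is a listed endpoint with the same censoring rules in SAP 2.8.3. It handles stopping differently: someone who stops without a response, and not because of progression or death, is censored at their final on-treatment PCR. The rates count the same patient as a non-responder. The two outputs would therefore differ even with no baseline responders.
- The resistance subgroup in SAP 2.2.1 (baseline ratio above 10%) contains no baseline responders, but it also leaves out every non-responder at or below 10%.

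**The case against.** The strongest reply is that the rule is determinate. Level, time point, analysis set and denominator are all given, every patient is classified one way, and a whole-FAS rate of being in response by a given week is a legitimate summary. That stands. A reader might infer that the rates are undefined or wrong; they are neither. What is missing is the label and the companion rate.

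Second, the time-to-response analysis excludes baseline molecular responders and reports cumulative incidence at the same weeks, so the plan is not without a view of new response. That also stands, with the limit on censoring shown above.

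Third, baseline counts may already be planned. SAP 2.1.1 slots molecular assessments over time, Table 2-1 has a baseline row, and SAP 2.8.3 mentions response categories by time point. The SAP does not say that baseline is among those time points, so this is likely cover rather than certain cover.

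Fourth, the consequences are small. The rates are secondary, nothing is tested, and the study is not powered to compare cohorts. A reader might infer a biased comparison of Cohorts A and B. Allocation between them is random, so their baseline shares would differ only by chance. Cohort C is not randomized, but there baseline MMR is least likely.

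Finally, the note might be feared to remove patients from duration, PFS or OS as well. The text does not support that: SAP 2.8.2 lists time to event separately from those three.

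**Conclusion.** The point holds as one of labelling and interpretation, and it is minor. Followed as written, the four molecular rates combine maintained with new responses and are presented as achievement, whereas Protocol 1.1.2.2 labels the earlier study's MMR rate without T315I as achieved or maintained. The exclusion note needs to name the level it applies to. It can be read as an exception under the 'unless stated otherwise' clause, but it is not written as one.

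A reader might infer from the table of excesses that the reported rates will be inflated by several points. The documents do not support that. The share at each level at baseline is not given and may be zero, the stand-in values for r are themselves mixed rates, and b(1 − r) assumes that every baseline responder keeps the level for one sample. What can be said without assuming b is the per-patient step: 2.2 points in Cohort A or B and 4.0 in Cohort C. No hypothesis test, sample size or primary endpoint is affected.

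**What to change.** 1. Keep the full-FAS rate for MR2, MMR, MR4 and MR4.5, and label it *achieved or maintained*.
2. For each level and time point, add the rate among FAS patients not at that level at baseline, with its Clopper-Pearson interval.
3. Give the number of patients at each level at baseline by cohort, unless the planned response-category summary already shows it.
4. Make the exclusion of baseline responders level-specific, so that a patient in MR2 but not MMR at baseline stays in time to MMR, MR4 and MR4.5. Limit it to time to molecular response and state it as an exception to the FAS in that section.

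The cost is SAP wording, one extra denominator per level and possibly one count table; baseline RQ-PCR is already collected. The denominators shrink, the intervals widen and the new-response rates will look less favourable. The SAP history shows Amendment 1.0 before the primary database lock and Amendment 2.0 before a later interim lock, so any analysis added after the Week 24 results should be labelled post hoc.

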Time to achieve a specific response level will be analyzed using the Kaplan-Meier Product-Limit method. Patients who are known to be without achieving that response level will be censored at the last adequate assessment. Estimates of the 25th, median and 75th percentile of the time to achieve a response level and their 95% confidence intervals will be provided, if applicable.

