### Baseline

For safety & efficacy evaluations, the last available assessment on or before the date of start of study medication of asciminib (40 mg BID, 80 mg QD & 200 mg BID) is taken as “baseline” assessment. For pre-dose electrocardiogram (ECG), the last available assessment before the treatment start date/time is used for baseline.

For ECGs, where study requires multiple replicates per time point, the average of these measurements would be calculated for baseline (if not already available in the database).

In rare cases where multiple laboratory measurements meet the baseline definition, with no further flag or label that can identify the chronological order, then the following rule should be applied: If values are from central and local laboratories, the value from central assessment should be considered as baseline.

If patients have no value as defined above, the baseline result will be missing.

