### **2.8.3 Handling of missing values/censoring/discontinuations**

#### **MMR rates by specific time points:**

Patients without any documented response for which an evaluable response assessment was never provided will be considered as non-responders for the period of time up to that time point.

**Molecular response category by specific time points:** The category “Missing” will be assigned to patients for whom an evaluable response assessment was never provided.

**Time to MMR:** For patients in the FAS who have not experienced any MMR, the time will be censored as follows in the Kaplan-Meier analysis:

If a patient does not achieve the specified response before the cut-off date for the analysis, censoring time will be the last molecular assessment (PCR) date on treatment prior to the cut-off date or the EoT visit, whichever comes first.

If a patient discontinues study treatment prior to achieving a response for a reason other than disease progression or death, then the patient will be censored at the last molecular assessment (PCR) date on treatment prior to the cut-off date or the EoT visit, whichever comes first.

If a patient discontinues study treatment prior to achieving a response due to progression or death, then the censoring time will be set to the longest follow-up time in the treatment group, that is, consider the response is impossible to reach.

In case no on-treatment response assessment was performed, the patient will be censored at day 1.

[figure not shown]
**Duration of MMR:** For patients who have not experienced any event (loss of MMR, progression to AP/BC, or CML-related death), the duration will be censored at the last molecular assessment (PCR) date on treatment.

[figure not shown]
**PFS:** For patients who have not experienced protocol defined event (disease progression to AP/BC or death from any cause), the patients will be censored at the date of last study assessment (PCR, cytogenetic, hematologic or extramedullary) before the cut-off date.

**OS:** Patients who are alive at the time of the analysis data cutoff date will be censored at the date of last contact (see Section 2.1.1) before the cut-off date.

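### The SAP's baseline-response exclusion names no response level, so as written it removes patients still at risk for MMR, MR4 and MR4.5 from the time-to-response analyses

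*SAP*

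**What the plan says.** SAP 2.8.2 sets out the response rates by week and closes that block with the note "Patient(s) who have reported for molecular response(s) at baseline will not be included in time to event analyses". Directly below, the subsection on time to response says "The analyses will be performed using FAS by cohort" and does not repeat the exclusion.

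The wider statements on population are:

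- SAP 2.2: "All the secondary efficacy endpoints will be analyzed using FAS".
- SAP 2.8.2, opening: "For all secondary efficacy analyses, the Full Analysis Set (FAS) will be used, unless stated otherwise".
- SAP 2.8.3, time to MMR: "For patients in the FAS who have not experienced any MMR, the time will be censored as follows in the Kaplan-Meier analysis". No baseline exclusion is mentioned.

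Baseline is "the last available assessment on or before the date of start of study medication" (SAP 2.1.1). For the by-week rates, "patients will be considered as responder if he/she achieves the particular response at least once by the specific timepoint", and nobody is removed for a response at baseline.

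Protocol 12.5.2.2 measures time to response from the first dose and gives a censoring rule for non-responders: "Patients who are known to be without achieving that response level will be censored at the last adequate assessment". It has no baseline exclusion. SAP section 4 states that the protocol's analyses are unchanged.

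**The concern.** Leaving a patient already in MMR out of time to MMR is sound, because that patient is not at risk for the event. The note goes further: any molecular response at baseline is enough, whichever level is being analysed. SAP Table 5-3 puts MR2 at or below 1% and MMR at or below 0.1%. A patient between the two has a molecular response at baseline and is still fully at risk for MMR, MR4 and MR4.5.

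Such patients can enrol. Protocol 5.1 accepts intolerance of the last TKI with no minimum transcript level, and it counts loss of MMR as failure, which allows entry above 0.1% but at or below 1%. Protocol 1.1.2.2 reports the earlier asciminib study's MMR results as responses reached or kept, which indicates that baseline responders occur in this setting.

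At stake is what the time-to-MMR and deeper-response curves describe. They would be labelled FAS but would cover only patients with no molecular response at baseline. The Kaplan-Meier incidences at Weeks 12, 24, 48 and 72 would sit beside by-week rates drawn from a different population.

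**Working it through.** **1. The wording, side by side.** Where the SAP means one level, it says so: the by-week rule refers to the particular response, and the censoring rules in 2.8.2 and 2.8.3 refer to the specified response. The note has no such qualifier. A programmer who follows it literally builds one exclusion flag and applies it to every level. One who follows the FAS sentence below it excludes nobody. The text does not settle which risk set is meant.

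**2. Cohort size.** The plan's figure reproduces: 1.96² × 0.18 × 0.82 / 0.12² = 39.4, rounded up to 40, and 40 / 0.9 = 44.4, rounded up to 45. The point does not depend on this calculation; 45 is used below as the size of Cohort A or B.

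**3. Bracketing the effect.** The documents give neither the baseline transcript distribution nor MMR incidence by baseline level. The following are assumptions:

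- 10% of 45 (4 patients) are already in MMR at baseline, so a level-specific rule leaves 45 − 4 = 41 at risk for MMR.
- 10%, 20%, 30% or 40% of 45 (4, 9, 14 or 18 patients) are MR2-only at baseline.
- MMR incidence is 25% in patients above 1%, and 40% or 60% in MR2-only patients.

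With h patients above 1% and m MR2-only patients:

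- incidence under the note = 0.25, with n = h
- level-specific incidence = (0.25h + pm) / (h + m), with p = 0.40 or 0.60
- by-week FAS rate = (0.25h + pm + 4) / 45, counting the 4 baseline-MMR patients as responders

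Example, 20% MR2-only and p = 0.40: (0.25 × 32 + 0.40 × 9) / 41 = 11.6 / 41 = 28.3%. The by-week rate is 15.6 / 45 = 34.7%.

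| MR2-only | n under note | n level-specific | Under note | Level-specific | Understatement (points) | By-week FAS rate |
|---|---|---|---|---|---|---|
| 10% (4) | 37 | 41 | 25% | 26.5–28.4% | 1.5–3.4 | 33.0–34.8% |
| 20% (9) | 32 | 41 | 25% | 28.3–32.7% | 3.3–7.7 | 34.7–38.7% |
| 30% (14) | 27 | 41 | 25% | 30.1–37.0% | 5.1–12.0 | 36.3–42.6% |
| 40% (18) | 23 | 41 | 25% | 31.6–40.4% | 6.6–15.4 | 37.7–45.7% |

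**4. No difference between groups.** With p = 0.25, the level-specific figure is also 25% and there is no bias. Only precision is lost. The approximate 95% half-width, 1.96 × √(0.25 × 0.75 / n), ignoring censoring, is 0.133 at n = 41, 0.150 at n = 32 and 0.177 at n = 23.

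**5. Rates against curves.** Even a level-specific rule leaves a gap to the by-week rates, because those rates keep patients already at the level. That gap is easily explained by the reported number excluded. The further gap between the note and the level-specific rule comes from dropping patients who are at risk.

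**The case against.** The strongest reply is that the note can be read distributively: for each level, leave out those already at that level. The SAP does analyse the levels one at a time, so this may be the intent. It is not what the sentence says, though, and a rule that needs that reading should state it.

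Second, SAP 2.8.2 uses the FAS unless stated otherwise, and the note states otherwise. That answers the general FAS default. It does not answer the FAS sentence in the subsection the note governs. The protocol is silent on baseline responders rather than opposed to excluding them, and it leaves detailed methods to the SAP. Even so, an exclusion that changes the analysed population belongs in section 4.

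Third, a curve among patients with no baseline response is a valid estimate for that group. This stands, but the SAP does not say that this group is the target.

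Three stronger readings are tempting and are not supported:

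- **Exclusion from PFS and OS.** Protocol section 12 uses time to event as a general Kaplan-Meier term, so a reader might extend the note to survival. SAP 2.8.2 lists time to event apart from duration, PFS and OS; PFS and OS have their own rules with no exclusion; and the note stands directly above the time-to-response subsection. Part of the SAP's general conventions is redacted, so a definition there cannot be ruled out.
- **Harm to time to CHR.** Read literally, the note removes patients from time to CHR on a molecular criterion. Nothing shows that patients at or below 1% would lack CHR at baseline, and SAP 5.3.1 treats values below 1% as equivalent to complete cytogenetic response.
- **Damage to the randomised comparison.** Random allocation serves patient selection only, no hypothesis is tested, and summaries are by cohort. A level-specific rule also excludes some FAS patients.

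**Conclusion.** The point holds for the time-to-response analyses. Taken as written, the note removes patients in a shallower baseline response from time to MMR, MR4 and MR4.5 while they are still at risk. It contradicts the FAS sentence that follows it, puts the Kaplan-Meier incidences and the by-week rates on different populations, and is not declared in section 4.

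Its size cannot be derived from the documents. Under the assumptions shown, 4 to 18 at-risk patients per 45-patient cohort are lost. MMR incidence among at-risk patients is understated by roughly 1 to 15 points if MR2-only patients reach MMR more often than the others, and by nothing if they do not. These figures show the range of a possible effect and do not predict it.

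This should be fixed, but it is not critical. The by-week rates carry no exclusion, the affected curves are descriptive secondary outputs, and the primary safety analysis and sample size do not depend on them.

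**What to change.** Replace the note with a level-specific rule, for example:

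*For time to a given molecular response level, patients already at that level or deeper at baseline are excluded from that analysis only; a baseline molecular response does not exclude a patient from time to CHR, PFS or OS.*

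The second half is a clarification, since the SAP's own text already points that way for PFS and OS.

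Then:

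- amend the FAS sentence in the time-to-response subsection of SAP 2.8.2 to refer to this rule, and do the same for time to MMR in 2.8.3;
- report the number excluded for each level and cohort beside each curve;
- record the exclusion in SAP section 4.

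The cost is a few lines of SAP text and a separate denominator for each response level. No new data are needed.
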